Cover Page

Title: The Effects of Yoga on Psychological and Physiological Health in a Population Based Cohort

The main statistical analysis plan is on page 10 of the study protocol

Lund University IRB Approval Number: 2015/610

NCT Identifier Number: Not yet assigned

Document Date: 03/02/2018

PROJECT PLAN

YOGA PRESCRIPTIONS (YOGA PÅ RECEPT) – STUDY 2 **THE EFFECTS OF YOGA ON PSYCHOLOGICAL AND PHYSIOLOGICAL HEALTH IN A** **POPULATION BASED COHORT**

The general purpose of this study is to evaluate the benefits of yoga as a ‘mind-body’ practice, by measuring its effects on health-related psychological and physiological variables. We also aim to investigate whether a relation exists between subjective (psychological) and objective (physiological) measures, with a particular focus on stress as the primary outcome. Further, we intend to include measures of mindfulness, breathing and experiential avoidance – variables that may explain the mechanism by which yoga exerts its putative health-promoting effect. Similar to our previous research on the topic of yoga and health (Dnr 2014/906 & 2015/247) we expect that changes in stress, anxiety, sleep problems via yoga practice will lead to improved health outcomes among individuals reporting moderate to high levels of perceived life stress.

Background

Stress and worry in everyday life are common features of Western society, wherein demands to constantly achieve and not get ill are high - in the workplace, at school or at home. Evolutionarily, stress is a biological mechanism, necessary for all living creatures when being exposed to threats in the immediate environment, tapping the fight-or-flight-response via activation of the sympathetic nervous system (Kroese, 2000; Wallace, 2009). However, when exposed to stress during prolonged periods of time, the immune system is affected, leading to physiological as well as psychosocial problems (Kroese, 2000). The consequences of untreated high stress can not only turn into reduced job capacity, work roles conflicts, etc., but also into a mental illness such as an anxiety disorder or/and depression, which, in many cases, results in long periods lost from work (Hejbel, 2012).

Stress is caused by many different factors. When a person perceives that the demands upon him/herself are higher than the resources to meet those demands, he/she experiences psychosocial stress (Morone et al., 2012). A way of explaining the psychological aspects of stress is that it emerges in the collision between the individual’s expectations and the actual experience of the present moment, creating feelings of being stressed when these do not match (Kroese, 2000). Kroese (2000) also argues that underlying the stress response is usually some sort of worry, often related to feeling a lack of control. Cohen et al. (1983) regards the stress response as not merely dependent on the intensity or number of stressful events, but also on personal and contextual factors. How an individual appraises events occurring in his or her life will affect the level of perceived stress (Cohen et al, 1983; Kroese, 2000).

Different coping strategies may be helpful in managing stress. One of these strategies, acceptance, has been shown to be powerful in helping to ameliorate the stress reaction (Kroese, 2000; Schenström, 2007). Being able to accept that what is going on in the surrounding environment is not always in accordance with one’s expectations can be a powerful tool in coping with stress. Acceptance is sometimes interpreted as passive

resignation (Baer et al., 2006); however, it has more to do with allowing oneself to see and endure reality as it is, without avoidance or judgments - to accept the full experience while refraining from self-criticism and impulsive reactions (Baer et al., 2006; Kåver, 2004; Gunaratana, 2011). Furthermore, mindfulness, a broader concept that encompasses acceptance, can help change a person's approach toward being able to focus his/her energy on the things that are changeable and within one's control (Kroese, 2000; Schenström, 2007).

One common and recommended strategy to manage stress is to exercise regularly (Camiletti-Moirón et al., 2013). The up-to-date scientific knowledge on how to prevent and treat various diseases and conditions using physical activity is summarized in *Physical Activity in the Prevention and Treatment of Disease* (2010). However, in order to cultivate acceptance, improvements in mindfulness - an important segment in all yoga classes- are needed. In the above mentioned book, yoga is named among the various types of physical activity and exercise; however, the main focus in the majority of yoga classes is on both body and mind, with focused breathing acting as a physiological compass that reflects one's current emotional and mental state (Brown & Gerbarg, 2009). Thus, yoga practice not only elicits physical motion, but it is also a method for cultivating mindfulness and acceptance. Morone et al. (2012) carried out a phenomenological study to identify which themes appeared to be essential in the process of applying mindfulness as a method to cope with psychosocial stressors. The four identified themes were *awareness*, *coping*, *serenity* and *change in perspective*, pointing toward an increased ability in the participants to be self-aware and self-reflective, and being able to stop and focus on the moment instead of ruminating on the past or worrying about the future.

Ross and Thomas (2010) reviewed studies comparing the effects of yoga (i.e., physical activity as a type of mindfulness practice) and exercise (i.e., physical activity without emphasis on mindfulness) on a variety of health conditions. The authors concluded that yoga may be as effective as or better than ordinary exercise at improving a variety of health-related outcomes. Given that yoga is multi-dimensional; that is, it includes aspects of exercise, breath work, concentration, and meditation, it is not surprising that researchers have found positive results in so many different areas (e.g. relieving physical symptoms, lowering blood pressure, improving perceptions of mood and anxiety among others. For review, please see Ross & Thomas, 2010).

To illustrate, exercise has been recognized as a key component in cardiac rehabilitation. Yoga, when added to usual cardiac care in randomized trials, has been shown to be significantly better than usual care at improving blood lipid levels (Manchanda et al., 2000), decreasing markers of inflammation (Pullen et al., 2008), and in reducing the number of revascular procedures (Manchanda et al., 2000). These findings are particularly salient to the present study as the epidemiology of carotid artery disease is the overarching focus of the Malmö Diet and Cancer Cardiovascular Cohort and its offshoot, the Malmö Offspring Study, from which our participants will be primarily recruited.

Yoga has also shown a positive effect on psychological problems, including depression and anxiety (Kinser et al., 2013). Several studies have shown a significant decrease in stress levels even over short time periods of yoga practice and mindfulness (Brisbon & Lowery, 2009; Carmody et al., 2009; Chambers Christopher et al., 2006; Cowen & Adams, 2005; Morone et al., 2012; Salmon et al., 2009). Streeter et al. (2010) compared a group of yoga practitioners to a group of people engaging in walking as exercise, showing greater improvement of mood along with greater decreases in anxiety in the yoga group as compared

to the walking group. They also found that the behavioral intervention (i.e. yoga) showed a positive association between changes in thalamic GABA levels and improvements in mood and anxiety, compared to the walking group. In sum, the practice of yoga and mindfulness seems to provide individuals with powerful tools to cope with daily stress and related problems.

Aims

The primary purpose of this study is to evaluate the effects of yoga on: 1) psychological health, specifically measured as stress level, stress coping strategies, depression, anxiety, well-being, life harmony, diet, and sleep quality; and 2) physiological health, specifically measured as blood plasma and serum stress markers (e.g., hormones, inflammation), blood plasma stress-related indicators (i.e., metabolic and cardiovascular function), and non-invasive clinical measures of stress-related indicators (i.e, cardiovascular and autonomic nervous system function) including blood pressure, arterial stiffness (via pulse wave velocity), and heart rate variability (via electrocardiogram), as well as digestive health via gut microbiota fecal sampling. Further, we intend to explore whether any changes in coping strategies (breathing, mindfulness) as a result of yoga practice may correspond to predictable changes in well-being.

Method

Participants

We plan to conduct a randomized controlled field experiment. In order to properly evaluate the effects of the intervention statistically, we will recruit approximately 120 individuals (please see power analysis below). Study participants will be recruited primarily from the ongoing Malmö Offspring Study (MOS; Dnr 2012/594) which takes place at the Clinical Research Unit at Skånes University Hospital in Malmö (Klinisk Forskningsavdelning på Skånes universitetssjukhus i Malmö). MOS is an inter-generational study where all children and grandchildren of individuals in the Malmö Diet and Cancer Cardiovascular Cohort (MDC-CC; n=6103) are invited to participate. The MDC-CC is a population-based study that investigates the epidemiology of carotid artery disease (LU 51-90 and Dnr 2009/633; Melander, et al., 2009, 2012). Individuals participating in MOS who have indicated an experience of chronic stress during the past year will be contacted by the research team. Other individuals visiting the Clinical Research Unit and/or members of the community are also eligible to participate in the study according to the inclusion/exclusion criteria (please see below).

Procedure

1. Telephone and In-Person Recruitment and Screening

Recruitment will be accomplished in two ways, 1) via telephone, and/or 2) in person. Telephone recruitment will be directed to participants in the Malmö Offspring Study (MOS) as described above. For individuals in MOS indicating a chronic experience of stress within the past year, information letters will be sent (see Appendix 3). Then they will be contacted by a person employed by the research project. During the telephone call, information about

the current yoga study, as described in the information letter in the Appendix 3 and Appendix 4:1 will be given, and the person will be asked if he/she is interested in participating. The telephone interviewer will also ask questions related to the inclusion/exclusion criteria described below. In-person recruitment will be directed to individuals visiting the Clinical Research Unit at Skånes University Hospital in Malmö who indicate high stress to the personnel. They will be orally given the same information as during the telephone interview previously described. Recruitment will take place over an approximate 2-month period.

Inclusion criteria:

1. A score on four items of the Perceived Stress Scale (PSS; Cohen et al., 1983) between 8-16, thereby indicating a current stress experience of at least moderate level (please see Appendix 5:12).
2. Ability to participate in the intervention during the time-period.
3. Comprehensive in Swedish (the intervention will be in Swedish).

Exclusion criteria

1. Ongoing yoga practice or any regular practice of yoga or meditation within the last 6 months.
2. Any known physical limitations that may prevent light physical activity (yoga postures).

When a person qualifies for the study, an appointment will be scheduled for him/her to come to the Clinical Research Unit at Skånes University Hospital in Malmö for the initial tests to be taken (see Measures below). The name of each participant will only be registered on a single master list in combination with a numeric code to ensure participant anonymity (please see Ethical Considerations below for further detail). Numeric codes will be used throughout the remainder of the study to identify participants. Additionally, the master list will provide the randomly generated number indicating which study group he/she is assigned to. Each person will be randomized at the individual level to one of the following conditions:

- 1) Group 1: Stress education + Yoga (SED_YOGA). Education about stress plus yoga practice, 2 times per week for 5 weeks.
- 2) Group 2: Yoga (YOGA). Yoga practice, 2 times per week for 5 weeks.
- 3) Group 3: Control (CONTROL). Education about stress plus yoga practice, 1 session after the 5-week main study is completed.

2. First Appointment at the Clinical Research Unit (pre-testing)

At the first appointment, participants will be given a detailed information letter to read about the study and his/her participation (please see Appendix 4:1). Participants will also have the opportunity to ask any questions about the study and his/her participation. He/she will then be given the informed consent document to read and sign (please see Appendix 4:2). When informed consent is given, a copy will be provided to the participant, and the study measurements will begin.

Measures

Physiological measures:

Physiological measures will be carried out at the beginning of the appointment in order to capture, in particular, fasting blood samples. The full battery of physiological measures entails:

- 1) Fasting blood sampling (serum and plasma). Blood sampling will be performed via venipuncture which involves extracting venous blood through a small sterile needle and collection in a vacutainer (sterile glass or plastic tube). A total of 3 tubes will be collected for each participant, amounting to a total of 65ml of blood per person. Blood samples will then be sent to a biobank. A biobank is a freezer (-80 degrees) where biological samples are stored (please see Ethical Considerations for further details). Blood analysis will include stress hormones, inflammatory biomarkers, metabolic profiling, cardiometabolic biomarkers, cholesterol, triglycerides, creatinine, catecholamines (noradrenalin and adrenalin), renin, cortisol, and glucose concentration.
- 2) Fasting and 120-minute glucose tolerance test. The glucose tolerance test determines how the body responds to glucose (sugar). After a fasting blood sample is taken (see above procedure), participants will be asked to drink a liquid containing glucose. A second blood sample will be taken 120 minutes later.

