- 10) The Brief Experiential Avoidance Questionnaire (BEAQ; Gámez et al., 2014) consists of 15 items used to assess behavioral avoidance (situational avoidance of physical discomfort and distress), distress aversion (non-acceptance of or negative attitudes toward distress), procrastination (delaying activities that may cause distress), distraction/suppression (attempts to ignore or suppress distress), repression/denial (distancing and dissociating from distress), and distress endurance (willingness to engage in behavior that is consistent with one’s values even when in distress). Items are rated on a 6-point scale ranging from 1 (*strongly disagree*) to 6 (*strongly agree*). The scale shows evidence of good internal consistency with alpha coefficients ranging from .80 to .89 (Gámez et al., 2014).
- 11) The Yogic Breathing as Stress Coping Scale. We constructed a 4-item measure, the Yogic Breathing as Stress Coping Scale (YBSC), to evaluate how often individuals use breathing as a coping strategy when they experience a stressful event. The instruction, *What do you generally do when you experience stressful events?* was adapted from the COPE scale (Carver et al., 1989). The four items are as follows: *I take several deep, calming breaths; I breathe deeper and calmer; I focus on my breathing; I concentrate on my breath.* The four items are rated on a five-point Likert scale from 1 (I usually don’t do this at all) to 5 (I usually do this a lot).

Participants will be asked to wait (if needed) until a total of 2 hours have passed since their fasting glucose tolerance test, so that a 120-minute measurement of plasma glucose concentration can be acquired. Following this, participants will be invited to a quiet area/room where breakfast will be provided free of charge. After breakfast, participants will complete the psychological measures and be instructed by a Clinical Research Unit staff member on how to use the sphygmomanometer described above (the portable, digital blood pressure machine). Participants will also be given a container with lid to collect a fecal sample at home. Prior to leaving their appointment, participants will be given an information letter about their yoga practice (Please see Appendix 4:3-4:5), and they will be given a free yoga mat to bring to class (exception: Control group participants will receive their yoga mat

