during the workshop, please see below). Participants are asked to return the sphygmomanometer and fecal sample to the Clinical Research Unit the following day.

3. Yoga Interventions – 5 weeks

Group 1: Stress education + Yoga (SED_YOGA)

Stress education + Yoga brings together education about stress, mindfulness and yoga practice. It will involve weekly group meetings, homework (please see Appendix 4:6), and yoga postures. Stress education and mindfulness will make up one portion of the intervention. This will take place in a group lecture format and shall be conducted by a mental health professional(s). Yoga practice in a group format will make up the second portion of the intervention. The word yoga means ‘to yoke’ or ‘unite’ in the sense that it is a practice of connecting the mind with the body. Yoga thus focuses on mental and physical strength building exercises and postures, and in this study, will be lead by a trained yoga instructor(s). More specifically, yoga practice will involve controlled breathing, prescribed body positions, and meditation, with the goal of attaining a state of relaxation. Instructors will lead yoga practitioners in and out of yoga postures (poses) verbally throughout the sessions. Stress education + Yoga will be held 2x/week in the evenings for 5 weeks.

Group 2: Yoga only (YOGA)

The Yoga only group will include the same yoga practice as described above for Group 1, but it will not include the stress education component.

Group 3: Control (CONTROL)

The control group will not participate in any yoga practice for the duration of the research study. However, because these participants had indicated moderate to high levels of stress during study recruitment, we want to provide them with an introduction to yoga, after the study is completed. Therefore, each control group participant will be invited to a 3-hour yoga workshop directly following the 5-week study period. This workshop will include education about stress and mindfulness as well as an introduction to yoga practice. Similarly to Groups 1 and 2, participants in the Control group will receive a free yoga mat.

Approximately one week before the yoga intervention is due to end, participants will receive a letter by mail indicating their second appointment time at the Clinical Research Unit (please see Appendix 4:7-4:8).

4. Second Appointment at Clinical Research Unit (post-testing)

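### The baseline home blood pressure, and any home-collected fecal sample, is taken after the letter and yoga mat have made the group evident

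*Combined protocol and SAP*

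**What the plan says.** The project plan describes the sequence under Procedure, steps 1 and 2.

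- **Step 1, recruitment and screening.** Names and codes share one list: "The name of each participant will only be registered on a single master list in combination with a numeric code". The same list carries the allocation: "Additionally, the master list will provide the randomly generated number indicating which study group he/she is assigned to". The step ends with "Each person will be randomized at the individual level to one of the following conditions". No time is given for the draw.
- **Step 2, first appointment.** Consent comes first: "When informed consent is given, a copy will be provided to the participant, and the study measurements will begin". The physiological battery, including fasting blood, opens the visit. The 120-minute glucose sample and breakfast follow, and then the questionnaires: "After breakfast, participants will complete the psychological measures".
- **End of step 2.** "Prior to leaving their appointment, participants will be given an information letter about their yoga practice", with a reference to Appendices 4:3 to 4:5. A free mat is given at the same point, with an "exception: Control group participants will receive their yoga mat" at the later workshop.
- **After the visit.** "Participants are asked to return the sphygmomanometer and fecal sample to the Clinical Research Unit the following day". The Measures section and Ethical Considerations also allow the fecal sample to be given at the hospital.

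The section on sample size and power defines every outcome as the difference between the pre-test and post-test values. Ethical Considerations says that the name list is kept locked at the Clinical Research Unit, away from other study papers. It also says that control participants may be dissatisfied with their assignment.

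**The concern.** A baseline should be measured before the participant can react to the assigned group. Here one part of the baseline is collected at home after the participant has been given, or not given, a mat and has read a letter about the coming weeks. Blood pressure is named in the Aims as a stress-related indicator, and it can plausibly respond to disappointment or anticipation. If the arms react differently in that first day, the pre-test values differ by arm for a reason unrelated to the intervention. The change score then carries that difference into the treatment contrast. Nothing in the stated analysis would detect or remove it.

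**Working it through.** The plan gives no figure to reproduce. The check is the order of events, followed by what a change score does with a shifted baseline.

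**Order of events at pre-test**

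| Measure | Relative to letter and mat | Arm evident to participant? |
|---|---|---|
| Fasting blood, 120-minute glucose | Before | Not shown |
| ECG and heart rate variability | Before (same clinic battery) | Not shown |
| Questionnaires, including the Perceived Stress Scale | Before | Not shown |
| Fecal sample given at the hospital | During the visit; order relative to letter and mat not stated | Not shown |
| Fecal sample collected at home | After | Yes |
| Home blood pressure | After | Yes |

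The mat is the firmer evidence of the reveal, because the text itself says that controls do not get one at this visit. It separates yoga from control but not one yoga arm from the other. The three appendix letters would do that if there is one per group, but the appendices are not in the supplied document.

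**Effect on the difference score**

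Let *b* be the arm difference in the home blood pressure baseline caused by knowing the group. Assume that the reaction has gone by post-test.

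- Change score, as planned: bias in the arm contrast = *b* in absolute size. With an assumed *b* = 2 mmHg, the bias is 2 mmHg.
- Baseline-adjusted model with equal variances and pre/post correlation *r*: bias = *r* × *b*. With assumed *r* = 0.5, 0.5 × 2 = 1.0 mmHg; with *r* = 0.7, 0.7 × 2 = 1.4 mmHg.
- If the reaction persists unchanged to post-test, it cancels in the difference: *b* − *b* = 0.

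The 2 mmHg and both correlations are assumptions; the documents give no value for any of them.

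**Direction**

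If disappointed controls read high at baseline, they show an inflated fall by post-test, which hides a yoga benefit. If anticipation raises the readings of yoga participants, their fall is inflated, which creates an apparent benefit. The documents do not show which would dominate.

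**The case against.** The strongest reply is that the exposure is narrow. Stress is the primary focus, and the Perceived Stress Scale is completed before anything reveals the group. So are the other questionnaires, the blood samples and the ECG. This stands, and it limits the point to home blood pressure and to fecal samples actually collected at home. For the fecal sample, no clear mechanism is offered by which knowing the arm for up to a day would alter gut microbiota.

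It is also fair to say that the magnitude is hypothetical and has no sign. In addition, the supplied text refers to a device described earlier, but the listed battery contains no such description. A clinic blood pressure reading may therefore exist as well. If it does and serves as the pre-test value, the home reading matters less.

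A reader might go further and infer three things that the documents do not support:

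- **Randomisation before consent.** The allocation appears under step 1 and consent under step 2, so the layout invites this reading. The sentence says what the list contains, not when the number is drawn. A pre-generated list opened at or after consent fits the text equally well.
- **Staff knowing the group in advance.** Someone must know the arm to give or withhold a mat, but that is at the end of the visit. The list is locked away, and nothing says that recruiters or assessors consult it. Locked storage is nevertheless not a description of allocation concealment, and no independent holder of the sequence is named.
- **Arm-related loss of people who fail to attend.** This needs both of the above. Participants who drop out before the visit have not been shown their group, so their own knowledge cannot drive the loss.

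**Conclusion.** The point holds for the home measures. On the sequence as written, the baseline home blood pressure, and any fecal sample collected at home, is taken with yoga or control assignment evident. An arm difference in that baseline that fades by post-test passes in full into the planned difference score. Its size and sign are unknown, and the 2 mmHg example only shows the mechanism.

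The conclusion rests on two inferences: that receiving or not receiving a mat tells participants their arm, and that the home reading is used as the pre-test blood pressure. The clinic baselines, including the primary stress measure, are not affected through participant knowledge. The timing of the draw relative to consent and access to the list are unstated; these are details to supply, not faults shown. The change is worth making because it closes a route to bias at almost no cost.

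**What to change.** 1. Give the group letter and the mat when the participant returns the sphygmomanometer and any fecal sample the next day. That return is already planned. Add a line on how the letter reaches anyone who does not return the device as asked.
2. State when the random number is generated, by whom, and who can see it. Release each allocation only after consent and after all baseline measures, including the home ones, are complete.
3. Hold the allocation in a file that uses codes only, separate from the name list. The plan destroys the name list after data collection, and a separate file also ensures that the allocation record remains.
4. Say whether a clinic blood pressure reading is also taken, and which reading is the pre-test value.

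The cost is that participants learn their group and class schedule one day later. No extra visit or measurement is needed.
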